### **6.1.3 Supply of study treatment**

Lutathera® (lutetium Lu 177 dotatate/ lutetium (Lu) oxodotreotide) will be supplied by the Sponsor.

As Lutathera production and shipment takes approximately 12 days, Lutathera first dose must be ordered immediately after confirming patient eligibility and enrollment.

The sterile 2.5% Lys-Arg solution will be provided by the Sponsor or compounded by the appointed Pharmacy (hospital or local pharmacy).

Antiemetics, SRI imaging agents, somatostatin analogues or any other supportive care medication are not considered investigational drugs and will not be supplied by the Sponsor.

## **6.2 Other treatment(s)**

### **6.2.1 Concomitant therapy**

All medications, procedures, and significant non-drug therapies administered after the patient was enrolled into the study must be recorded on the appropriate Case Report Forms, including somatostatin analogues, amino acid solution and antiemetic administration.

Each concomitant drug must be individually assessed against all exclusion criteria/prohibited medication list. If in doubt, the investigator should contact the Sponsor before enrolling a patient or allowing a new medication to be started. If the patient is already enrolled, contact the Sponsor to determine if the patient should continue participation in the study.

### **6.2.2 Prohibited medication**

Patients may not receive any other systemic therapy for the treatment of GEP-NET or PPGL (chemotherapeutic, biologic, or any investigational agent) other than Lutathera and somatostatin analogues during the study treatment period.

Localized therapy such as surgery or external beam irradiation may be performed on additional site(s), provided that it does not affect study endpoint assessment. For a major surgery, treatment with Lutathera must be temporarily discontinued and can be restarted after 12 weeks from the date of surgery.

Somatostatin and its analogues competitively bind to somatostatin receptors. Therefore, administration of long-acting somatostatin analogues should be avoided within 4 weeks prior to the administration of Lutathera. If necessary, patients may be treated with short acting somatostatin analogues during the 4 weeks until 24 hours preceding Lutathera administration.

There is some evidence that corticosteroids can induce down-regulation of SST2 receptors. Therefore, as a matter of caution, repeated administration of high doses of glucocorticosteroids should be avoided during Lutathera treatment. The use of glucocorticosteroids should also be avoided as preventive anti-emetic treatment. In the case where the treatments previously provided for nausea and vomiting are insufficient, a single dose of corticosteroids can be used, as long as it is not given before initiating or within one hour after the end of Lutathera infusion.

The absence of inhibition or significant induction of the human CYP450 enzymes, the absence of specific interaction with P-glycoprotein (efflux transporter) as well as OAT1, OAT3, OCT2, OATP1B1, OATP1B3, OCT1 and BCRP transporters in preclinical studies suggest that Lutathera has a low probability of causing significant other drug-drug interactions.

There is no restriction for concomitant medications during the follow-up period.

### **6.2.3      Rescue medication**

In GEP-NET cohort, subcutaneous, short-acting octreotide injections may be indicated for control of GEP-NET symptoms (i.e. diarrhoea and flushing) at the judgment of investigator in accordance with the manufacturer's prescribing information. Short-acting octreotide for symptom control may be administered (at home) at investigator's discretion and recommendation provided in [Section 6.2.2](#) should be considered. Short-acting octreotide will not be supplied by the Sponsor.

In the PPG cohort, an adequate alpha- and beta-blockade should be maintained to avoid acute symptoms of catecholamine release (i.e. hypertension, pallor, sweating, palpitations). The treatment of such symptoms should be done as per standard local practice and physician judgment according to prescribing information ([Section 4.5](#)).

### **6.2.4      SARS-CoV-2 vaccination**

Patients are allowed to receive approved SARS-CoV-2 vaccines (inactivated, viral-vector-, or mRNA based Sars-CoV-2 vaccines approved by the Health Authorities in the country). The decision for vaccination should be done on a case-by-case basis and at the discretion of the treating physician, with patient consent, and in alignment with institutional guidelines, if available.

Investigators are expected to evaluate potential risks/benefits in the context of individual patient characteristics and make an individualized decision for vaccination. Investigators should refer to the prescribing information for the SARS-CoV-2 vaccine planned to be used and/or follow local Health Authorities or institutional guidelines, if available.

Patients should be instructed to contact their GP and/or the study site in case of side effects after vaccination.

Vaccine must be reported as a prior/concomitant medication according to the protocol guidelines. Any AEs after vaccination must be monitored and reported in eCRF.

## **6.2.5      Restriction for study participants**

Before leaving the clinical site after Lutathera administration, patients will be instructed about radioactivity protection measures.

## **6.3      Participant numbering, treatment allocation**

### **6.3.1      Participant numbering**

Each participant is identified in the study by a Participant Number (Participant No.), that is assigned when the participant is screened and is retained for the participant throughout his/her participation in the trial. A new Participant No. will be assigned at every subsequent rescreening. The Participant No. consists of the Center Number (Center No.) (as assigned by the Sponsor to the investigative site) with a sequential participant number suffixed to it, so that each participant's participation is numbered uniquely across the entire database. Upon signing the informed consent form, the participant is assigned to the next sequential Participant No. available.

### **6.3.2      Treatment allocation**

No randomization will be performed in this study as this is a single-arm open-label study. All patients will receive Lutathera treatment, which will be allocated upon site ordering for each individual administration. Sites will be resupplied with amino acid solution based on recruitment rate.

## **6.4      Treatment blinding**

This is a single-arm open-label study: No treatment blinding will be implemented.

## **6.5      Dose escalation and dose modification**

No dose escalation is permitted in the study. For dose modification, see below.

### **6.5.1      Dose modification**

In order to minimize risk for each study subject, an accelerated analysis of dosimetry and safety data will be performed for each individual patient in the study, to enable the Investigator to take a decision for the next Lutathera dose(s).

Dose modification recommendations for toxicities (DMT) and dose modification recommendations according to dosimetry results will apply as discussed in [Section 6.5.1.1](#) and [Section 6.5.1.2](#), respectively. The results of dosimetry assessments (imaging and blood dosimetry) and safety assessments will be provided to and evaluated by investigators prior to administration of next therapeutic cycle to decide on a need for dose modification based on the rules described below.

Patients, whose treatment is interrupted or permanently discontinued, must be followed up at regular intervals. In case of treatment interruption, the frequency of follow-up visits until treatment is resumed is at the discretion of Investigator depending on the DMT type and severity. In case of permanent treatment discontinuation, patients will enter the Follow-up Period (see [Section 9.1.1](#)), with visits frequency as specified in the Assessment Schedule.

In case that dosimetry results exceed reference limits in individual patient(s) ([Section 4.2](#)), DSMB must be consulted to evaluate benefit risk for the patient and advise on whether dosing

can continue and at which level ([Section 6.5.1.2](#)). The DSMB charter will include the reference information needed for dose decision making (including data collected from the M&S study).

Appropriate clinical experts such as cardiologists, endocrinologists, hepatologists, nephrologists etc. should be consulted as deemed necessary.

### 6.5.1.1 Dose modifying toxicities (DMTs)

Management of severe or intolerable adverse drug reactions may require temporary dose interruption, extending the dosing interval from 8 weeks up to 16 weeks, dose reduction, or discontinuation of treatment with Lutathera.

For patients who do not tolerate the protocol-specified dosing schedule, dose adjustments are permitted to allow the patient to continue the study treatment.

The criteria for dose modifications of Lutathera for toxicities are outlined in [Table 6-4](#). The evaluation for potential DMTs will be done by Investigator based on local laboratory results from hematology and biochemistry tests done after each Lutathera treatment.

If a patient requires a dose delay of > 16 consecutive weeks of Lutathera from the intended day of the next scheduled dose, then the patient should be discontinued from the study treatment. In exceptional situations, if the patient is clearly benefitting from the study treatment (i.e. stable disease, partial response, complete response), and in the opinion of the investigator no safety concerns are present, after discussion with Sponsor Medical Monitor and/or DSMB, the patient may remain on the study treatment.

For each patient, a maximum of one dose reduction will be allowed after which the patient will be discontinued from the study.

All dose changes must be recorded on the appropriate electronic case report form (eCRF).

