  - Occurrence of an intercurrent disease (e.g. urinary tract infection);
  - Major surgery: wait 12 weeks after the date of surgery, then restart the treatment with Lutathera.

If a patient experiences DMT during Lutathera therapy, subsequent treatments with Lutathera are permissible, provided the DMT resolves within 16 weeks following the non-tolerated administration. After resolution of a DMT, a patient may receive subsequent planned treatment(s) at 50% of the standard treatment dose, if this is felt to be safe for the patient, or the risk-benefit assessment is favourable. If the same DMT recurs after treatment with the reduced Lutathera dose, no further Lutathera treatment will be given. If the DMT event does not reoccur, the next treatment is at full dose, if it is considered to be safe for the patient, or the risk-benefit assessment is favourable.

Dose modification recommendations for toxicities might be overruled by dose modification recommendations based on dosimetry, and vice versa, i.e. a dose modification should be applied based on toxicity grading, even if dosimetry values are within limits.

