### **6.5.2 Dose discontinuation**

The discontinuation of treatment with Lutathera is not a reason for patient's withdrawal from the study (reasons for the patient's withdrawal are discussed in [Section 9](#)). In case of a patient's withdrawal from the study treatment (based on either the patient's or the Investigator's decision), patients will undergo all exams scheduled for the End of Treatment (EoT) visit ([Table 8-2](#)) and continue into the Follow-up period.

If the treatment discontinuation occurs because of laboratory abnormality, or any evidence of toxicity, the Investigator will collect additional specimens for repeat or additional analyses, at intervals appropriate to the abnormality. The patient will be closely followed until sufficient information is obtained to determine the cause or the value regresses. Appropriate remedial measures should be taken and the response recorded in the eCRF.

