|                       |                  | 12. Blood collection for dosimetry includes 6 radioactive blood samples at the following time points: before the start of Lutathera infusion, at the end of Lutathera infusion, then at 2h, 6h, 24h and 72h after the end of Lutathera infusion.
13. On Day 1 of Cycle 1, safety biomarkers are assessed pre-dose.
14. Safety biomarkers are taken either at Week 7 of cycle 1 or pre-dose of cycle 2.
15. Safety Biomarkers are taken either at Week 7 of cycle 4 or at the EoT visit.
S = assessment to be recorded in the source documentation only and not recorded in CRF page.
* The last FU visit would be the EOS visit for patients who completed the long-term FU period; and a separate EOS visit should be planned for patients who discontinued from the study prior to completion of the long-term FU period. |                |               |         |               |         |         |            |         |         |  |                          |                          |                          |  |

Variations of  $\pm$  1 week are allowed for the visits during the Treatment period (including the window for Lutathera administration visits that should occur in 8 weeks from the previous dose  $\pm$  1 week), and during the Short-term Follow-up. The exception is the week when dosimetry assessments are performed – during the dosimetry week, all visits must occur on the Days specified in the [Table 8-2](#).

During the Long-term Follow-up, a visit window of  $\pm$  1 month is allowed.

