### **9 Study discontinuation and completion**

#### **9.1 Discontinuation and completion**

##### **9.1.1 Study treatment discontinuation and study discontinuation**

Discontinuation of study treatment for a participant occurs when study treatment is stopped earlier than the protocol planned duration and can be initiated by either the participant or the investigator.

The investigator must discontinue study treatment for a given participant if, he/she believes that continuation would negatively impact the participant's well-being.

Study treatment must be discontinued under the following circumstances:

- Participant/guardian decision
- Pregnancy
- Any situation in which study participation might result in a safety risk to the participant including unacceptable adverse event.

If discontinuation of study treatment occurs, the investigator should make a reasonable effort to understand the primary reason for the participant's premature discontinuation of study treatment and record this information.

Participants who discontinue study treatment or who decide they do not wish to participate in the study further should NOT be considered withdrawn from the study UNLESS they withdraw their consent (see [Section 9.1.2 'Withdrawal of Informed Consent' section](#)).

**Where possible, all patients who discontinue study treatment should return for the EoT/Early Termination Visit assessments, and continue into the full Follow-up period as indicated** in the Assessment Schedule. If they fail to return for these assessments for unknown reasons, every effort (e.g. telephone, e-mail, letter) should be made to contact the participant/pre-designated contact as specified for lost to follow-up ([Section 9.1.3](#)). This contact should preferably be done according to the study visit schedule.

If the participant cannot or is unwilling to attend any visit(s), the site staff should maintain regular telephone contact with the participant, or with a person pre-designated by the participant. This telephone contact should preferably be done according to the study visit schedule.

After study treatment discontinuation, if the patient is unwilling to perform all scheduled assessments, then at a minimum, in abbreviated visits, the following data should be collected at clinic visits or via telephone/email contact:

- Survival status
- New / concomitant treatments, including all antineoplastic therapies
- Adverse Events / Serious Adverse Events

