#### **9.2 Study completion and post-study treatment**

Study completion is defined as when the last patient finishes their last follow-up visit and any assessments associated with this visit have been documented and followed-up appropriately by the Investigator or, in the event of an early study termination decision, the date of that decision.

Following the end of treatment or early treatment discontinuation, patients will enter in the Follow-up Period unless unfeasible (e.g. consent withdrawal, patient lost to follow-up). Patient visits and assessments will be performed during the follow-up period as per the study schedule of assessments ([Table 8-2](#)) and [Section 9.1.1](#).

The last follow-up visit (5 years after the last dose of Lutathera) will be considered as End of Study (EoS) visit for each patient.

When the study planned enrollment is met, study subjects currently on study treatment or in the follow-up period will continue the study as per the study schedule of assessment ([Table 8-2](#)).

Study Treatment will not be provided to the enrolled patients after completion of the study as Lutathera is administered as 4 doses and this is a full regimen. No provision of Lutathera post-trial is considered necessary.

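### Protocol 6.5.1.1 takes a patient who would need a second dose reduction out of the study, where the rest of the protocol stops treatment only and keeps the 5-year follow-up

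*Protocol*

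**What the plan says.** Section 6.5.1.1 of the protocol limits dose reductions: for each patient, "a maximum of one dose reduction will be allowed after which the patient will be discontinued from the study". The paragraph before it deals with a dose delay of more than 16 weeks and uses a different term: "then the patient should be discontinued from the study treatment". The text after Table 6-4 also stops the drug only: "If the same DMT recurs after treatment with the reduced Lutathera dose, no further Lutathera treatment will be given".

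Other sections say what happens once Lutathera is stopped:

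- Section 6.5.1: "In case of permanent treatment discontinuation, patients will enter the Follow-up Period".
- Section 6.5.2: "The discontinuation of treatment with Lutathera is not a reason for" withdrawing a patient from the study.
- Section 9.1.1: patients who stop study treatment "should NOT be considered withdrawn from the study UNLESS they withdraw their consent".
- Section 9.2: "Following the end of treatment or early treatment discontinuation, patients will enter in the Follow-up Period unless unfeasible".
- Section 3 plans 5 years of follow-up after the last dose for everyone given at least one dose.

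The footnote to Table 8-2 describes leaving the study itself: "a separate EOS visit should be planned for patients who discontinued from the study prior to completion of the long-term FU period".

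**The concern.** Stopping treatment and leaving the study are different events in this protocol. The glossary allows a patient to do the first without the second, and describes premature withdrawal as the point after which no more assessments are planned. Section 6.5.1.1 uses the term for leaving the study where its neighbours use the term for stopping treatment, and the Table 8-2 footnote attaches an early End of Study visit to that term.

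The patient concerned has had repeated dose-modifying toxicity, and is therefore one of the most informative for the secondary objective on long-term safety. A site that followed the sentence as written would end that patient's follow-up for late effects such as secondary malignancy. The patient would also drop out of the laboratory and vital-sign summaries that SAP Sections 2.6.4 and 2.6.5.2 extend over the short-term and long-term follow-up.

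**Working it through.** The plan states no figure on this point, so the check is mainly a comparison of wording.

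**1. What each rule stops**

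| Place in protocol | Trigger | What ends |
|---|---|---|
| 6.5.1.1, delay paragraph | Delay of more than 16 weeks | Study treatment |
| Table 6-4, recurrent rows | Same toxicity again | Lutathera |
| 6.5.1.1, text after Table 6-4 | Same toxicity after the reduced dose | Lutathera |
| 6.5.1.1, reduction limit | One reduction already used | **The study** |

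Only the last row ends participation. Section 6.5.2 refers to Section 9 for the reasons for leaving the study, and Section 9.1.1 lists no reason connected with dose reduction.

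**2. Whom the sentence governs**

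Table 6-4 triggers a reduction at the first occurrence of each toxicity separately. Take a patient with this course:

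- After dose 1: first grade 2 thrombocytopenia. Dose 2 is given at 3.7 GBq.
- After dose 2: no recurrence. Dose 3 goes back to 7.4 GBq.
- After dose 3: first grade 3 neutropenia.

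No recurrent row applies, because neutropenia has not occurred before. The first-occurrence row for neutropenia directs dose 4 at 3.7 GBq after resolution. The reduction limit says that no second reduction is allowed and that the patient leaves the study. Two rules therefore apply to this patient, and they disagree on dosing as well as on follow-up. Deleting the limit would remove the cap; the sentence needs rewording.

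**3. What one such patient would miss**

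- Short-term visits at weeks 13, 19 and 25 after the last dose: 3.
- Long-term visits every 6 months over 54 months: 54 / 6 = 9.
- Total: 3 + 9 = 12 visits, over up to 60 months.
- Share of the cohort, with 11 enrolled by 14 December 2023 (Amendment 03): 1 / 11 = 9.1%.

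**4. Illustration for a late event**

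Assume that the adult MDS rates in Section 4.3 apply: 2% (Erasmus MC) and 2.3% (NETTER-1). The chance of seeing at least one case among n patients is 1 − (1 − p)^n.

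| p | n = 11 | n = 10 |
|---|---|---|
| 2% | 1 − 0.98^11 = 19.9% | 1 − 0.98^10 = 18.3% |
| 2.3% | 1 − 0.977^11 = 22.6% | 1 − 0.977^10 = 20.8% |

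Losing one patient costs 1 × 0.02 to 1 × 0.023, or about 0.02 expected cases. What is lost is one individual's late-safety record; the study's ability to detect MDS hardly changes.

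**The case against.** The strongest reply is that the protocol already settles the matter. Section 6.5.1 is the parent of the disputed text and sends patients who stop permanently into follow-up. Section 9.1.1 is the section on treatment and study discontinuation; it keeps them in the study and sets a minimum of data to be collected by telephone or email if they will not attend. The Table 8-2 footnote only schedules a visit and does not decide who leaves. Harm needs a site to follow one clause against all of these. This stands, and it is why the point is minor. It does not remove the contradiction, because the disputed sentence is an operative dosing rule that a site would consult in exactly this situation.

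A reader might go further than the documents allow in several ways:

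- *That the protocol means to end follow-up for these patients.* The sections listed above say otherwise, so a drafting slip is far more likely.
- *That the patient leaves after the first reduction.* The grammar permits this, but Table 6-4 and the text after it provide for a return to full dose.
- *That no other dosing rule covers a second, different toxicity.* The first-occurrence rows of Table 6-4 do; the problem is conflict, not silence.
- *That the patient would leave by a known month, before late effects appear.* The documents do not fix this. Section 6.5.1.1 speaks of stretching the interval to 16 weeks, but stops treatment only when the delay exceeds 16 weeks from the scheduled day.
- *That the SAP is indifferent because it only lists follow-up data.* That holds for adverse events (SAP 2.6.1), but not for laboratory data and vital signs (SAP 2.6.4 and 2.6.5.2).

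**Conclusion.** Wrong as written, minor. Section 6.5.1.1 contradicts its own preceding paragraph and five other protocol sections on follow-up, and it conflicts with the first-occurrence rows of Table 6-4 on dosing.

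The documents give no rate of second reductions, so I put no number on how many patients are exposed. The group is probably small. The consequence for each is up to 12 visits and up to 60 months of safety follow-up, if a site acts on the literal text. The MDS illustration rests on adult rates carried over to adolescents and on 11 patients; it shows a small effect.

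Primary endpoints and sample size are not affected. A patient facing a second reduction has already completed the first cycle, which supplies the primary safety data and, except where dosimetry was deferred to a later dose, the dosimetry. The sample-size statements concern 8 patients and do not depend on follow-up.

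**What to change.** Replace the sentence in Section 6.5.1.1 with wording such as:

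*Each patient may have at most one dose reduction for toxicity, whichever toxicity caused it. A patient who would need a second reduction, including under a different first-occurrence row of Table 6-4, will be permanently discontinued from study treatment and will enter the Follow-up Period (Section 9.1.1).*

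This keeps the limit, resolves the conflict with Table 6-4 and restores the follow-up that the other sections require. The words *for toxicity* fit the section in which the rule stands; reductions advised on dosimetry grounds remain under Section 6.5.1.2, and the sponsor should confirm that this is the intent.

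The cost is one sentence in the next written amendment, approved as Section 14.1 requires (sponsor, IRB/IEC and, where required, health authorities). It needs no new data and no SAP change.
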